13.6 Clinical Study Report

The Sponsor must ensure that a CSR for this study is prepared regardless of whether the study is completed or prematurely terminated.

The CSR will be written based on standards of the ICH Guideline for the "Structure and Content of Clinical Study Reports"(23). In certain circumstances, an abbreviated CSR may be acceptable. Submission of the CSR to the IEC will be complied with as requested by local requirements.

13.7 Financial Disclosure

Investigators and any designees are required to provide financial disclosure information to the Sponsor. In addition, the Investigators and designees must provide the Sponsor with a commitment to promptly update this information if any relevant changes occur during the course of the investigation and for one year following the completion of the study.

13.8 Publication and Disclosure Policy

This document contains information that is confidential and proprietary to the Sponsor. This information is being provided solely for the purpose of evaluation and/or conducting this study for the Sponsor. Disclosure of the content of this document is allowed only to study personnel, IEC, or duly authorized representatives of regulatory agencies for this purpose under the condition that confidentiality is maintained. The contents of this document may not be used in any other study, disclosed to any other person or entity without the prior written permission of the Sponsor. The foregoing shall not apply to disclosure required by any regulations; however, prompt notice must be given to the Sponsor prior to any such disclosure.

According to The Federal Act on Research involving Human Beings and the Ordinance on Clinical Trials in Human Research, the study will be registered and published in a WHO primary register or clinicaltrials.gov as well as in the supplementary federal database.

Confidentiality Statement

Data and information contained in this document are considered to constitute trade secrets and confidential commercial information, and the legal protections provided to such trade secrets and confidential information are hereby claimed under the provisions of applicable law. No part of this document may be publicly disclosed without the written consent of Philip Morris Products S.A.

13.9 Insurance

The Sponsor is responsible for AEs and health damage of the subjects that are associated with the investigational products which are used during the study, except for AEs and health damage of the subjects caused by a negligent or an intentional misconduct and/or significant deviation to the protocol of the Investigator or the clinical investigational site or the subjects. The Sponsor has taken out insurance to cover any bodily injury and property damage caused by the operations carried out by the insured.

Confidentiality Statement

Data and information contained in this document are considered to constitute trade secrets and confidential commercial information, and the legal protections provided to such trade secrets and confidential information are hereby claimed under the provisions of applicable law. No part of this document may be publicly disclosed without the written consent of Philip Morris Products S.A.

15 APPENDICES

Appendix A – Schedule of Events

Study Day	Day -22 to -2 Screening	Day -1 Admission	Day 1	Day 2	Day 3	Day 4	Day 5 Discharge ^q	Day 5 to 12 Safety Follow-Up ^o
Informed consent	•							
Information on the risks of smoking/advice on smoking cessation and debriefing on P3P	•	•					•	
Inclusion/exclusion criteria ^a	•	•						
P3P product demonstration	•							
Smoking history	•							
Readiness to comply to study procedures, including period of abstinence from any tobacco and nicotine containing products	•	•						
Intention to quit smoking in the next 2 months	•	•						
Demographics ^b , medical history, concomitant diseases	•							
Prior medication ^c	•							
Concomitant medication	•	•	•	•	•	•	•	•
Physical examination	•	•					•	

Confidentiality Statement

Data and information contained in this document are considered to constitute trade secrets and confidential commercial information, and the legal protections provided to such trade secrets and confidential information are hereby claimed under the provisions of applicable law. No part of this document may be publicly disclosed without the written consent of Philip Morris Products S.A.

Study Day	Day -22 to -2 Screening	Day -1 Admission	Day 1	Day 2	Day 3	Day 4	Day 5 Discharge ^g	Day 5 to 12 Safety Follow-Up ^h
Body height, weight and related BMI	•							
Vital signs ^d	•	•	•	•	•	•	•	
ECG ^e	•	•	•	•	•	•	•	
Spirometry	•						•	
Blood and urine sample collection for hematology, clinical chemistry, urine analysis safety panel ^f	•	•		•	•	•	•	
Blood sample collection for serology	•							
Urine drug screen	•	•						
Urine cotinine screen (dip stick)	•							
Alcohol breath test	•	•						
Urine Pregnancy test (females)	•	•					•	
trans-3'-hydroxycotinine and cotinine (CYP2A6 activity) in plasma ^g			•					
FTND questionnaire	•							
Enrollment		•						
P3P product test ^h		•						
Randomization ⁱ				•				
P3P product use.								
Fixed puffing in the morning with HPT followed by ad libitum use in the afternoon with HPT ^j			•	•	•	•		

Confidentiality Statement

Data and information contained in this document are considered to constitute trade secrets and confidential commercial information, and the legal protections provided to such trade secrets and confidential information are hereby claimed under the provisions of applicable law. No part of this document may be publicly disclosed without the written consent of Philip Morris Products S.A.

Study Day	Day -22 to -2 Screening	Day -1 Admission	Day 1	Day 2	Day 3	Day 4	Day 5 Discharge ^a	Day 5 to 12 Safety Follow-Up ^o
Blood sample collection for plasma nicotine ^k			•	•	•	•	•	
VAS-craving ^l			•	•	•	•		
Adapted mCEQ ^m			•	•	•	•		
Sensory Questionnaire ^m			•	•	•	•		
Cough assessment ⁿ		•		•	•	•	•	
AE/SAE recording ^o	•	•	•	•	•	•	•	•
Product events Malfunctions/Misuse		•	•	•	•	•		
Support during periods of smoking abstinence (as required)			•	•	•	•	•	
Weighing of P3P products ^p			•	•	•	•		

Abbreviations: Adapted mCEQ = adapted version of the modified Cigarette Evaluation Questionnaire; AE = Adverse event; BMI = Body mass index; ECG = Electrocardiogram; FTND = Fagerström Test for Nicotine Dependence (revised version); HPT = Human puffing topography; SAE = Serious adverse event; SQ = Sensory questionnaire; VAS= Visual Analog Scale.

- a. Prior to enrollment at Admission the following inclusion and exclusion criteria will be re-checked: **Inclusion Criteria:** Subject is not planning to quit smoking within 2 months, Subject is available during the study period and ready to comply with study procedures. **Exclusion criteria:** Subject has a positive alcohol test and/or the subject has a history of alcohol abuse that could interfere with the subject's participation in study, subject has a positive urine drug screen, subject uses estrogen containing medication, female subject who is pregnant or breast-feeding, female subject of childbearing potential who does not agree to use effective contraception. The following eligibility criteria will only be checked at Admission: subjects will not be included if they have received medication within 14 days or within 5 half-lives of the drug prior to Admission (whichever is longer) which has an impact on CYP2A6 activity.
- b. Sex, date of birth, race.
- c. All medication taken within 4 weeks prior to the Screening Visit will be documented. Prior medication which has an impact on CYP2A6 activity taken within 14 days or within 5 half-lives of the drug (whichever is longer) prior to Day -1 is an exclusion criteria.
- d. Systolic and diastolic blood pressure, pulse rate and respiratory rate. Assessed in the morning within 60 minutes prior to fixed puffing regimen and 60 minutes \pm 10 minutes after each product use period (fixed puffing regimen and *ad libitum* use).
- e. On Days 1 to 4 ECG, will be performed after fixed puffing regimen and after the *ad libitum* use period.

Confidentiality Statement

Data and information contained in this document are considered to constitute trade secrets and confidential commercial information, and the legal protections provided to such trade secrets and confidential information are hereby claimed under the provisions of applicable law. No part of this document may be publicly disclosed without the written consent of Philip Morris Products S.A.

- f. Blood samples should be taken after at least 6 hours of fasting, except at Screening where non-fasting samples can be used.
- g. Sample taken in the morning prior to product use.
- h. During the Admission Visit after enrollment, subjects will be asked to perform a product test with the use of up to 3 products of P3P 3.
- i. A subject can be randomized only after confirmation that there are no safety concerns for the subject to continue the study as judged by the Investigator. If a sufficient number of subjects are already randomized to the study sequences, any supernumerous subjects will be discontinued from the study prior to randomization.
- j. Subjects will use one variant of P3P on a given study day. They will use P3P with HPT recording in the morning at a fixed puffing regimen comprising of 12 puffs in total at a rate of one inhalation every 30 seconds (\pm 5 seconds). In the afternoon, subjects will use P3P with HPT recording *ad libitum* for 60 minutes. Subjects will use P3P 3 at Day 1 and P3P 1, P3P 2 and P3P 4 in a randomized sequence at Days 2, 3 and 4.
- k. A total of 10 blood samples will be taken for fixed puffing PK parameter estimation at Days 1 to 4. One blood samples will be taken prior to the product use (T_0 fix) 15 minutes \pm 5 minutes (T-1). Thereafter in relation to T_0 fix, blood will be drawn at the following time points: T1 after 2 minutes \pm 1 minute, T2 after 4 minutes \pm 1 minute, T3 after 7 minutes \pm 1 minute, T4 after 10 minutes \pm 1 minute, T5 after 15 minutes \pm 2 minutes, T6 after 30 minutes \pm 2 minutes, T7 after 1 hour \pm 5 minutes, T8 after 2 hours \pm 5 minutes, and T9 after 4 hours \pm 5 minutes.
- A total of 8 blood samples will be taken for the *ad libitum* PK parameter estimation at Days 1 to 4. One blood sample will be taken prior to product use (T_0 *ad lib*) at 15 minutes \pm 5 minutes (T-1). In relation to T_0 *ad lib*, blood will be drawn at the following time points: T1 after 10 minutes \pm 1 minute, T2 after 20 minutes \pm 2 minutes, T3 after 30 minutes \pm 2 minutes, T4 after 40 minutes \pm 5 minutes and T5 after 1 hour \pm 5 minutes, T6 after 2 hours \pm 5 minutes, and T7 after 4 hours \pm 5 minutes.
- A total of 5 blood samples will be taken at Day 5. Blood samples will be taken in relation to T_0 *ad lib* from the last product use at the following time points: T1 after 14 hours \pm 30 minutes, T2 after 16 hours \pm 30 minutes, T3 after 18 hours \pm 30 minutes, T4 after 20 hours \pm 30 minutes and T5 after 24 hours \pm 30 minutes.
- l. The VAS craving will be completed by the subject at Days 1 to 4. For the fixed puffing regimen the first assessment will be done 15 minutes \pm 5 minutes prior to T_0 fix, all other assessments will be done after T_0 fix, at 4 minutes \pm 2 minutes, at 10 minutes \pm 2 minutes, at 15 minutes \pm 2 minutes, 30 minutes \pm 5 minutes, 1 hour, 2 hours, 4 hours \pm 10 minutes each. For the *ad libitum* use period the first assessment will be done 15 minutes \pm 5 minutes prior to T_0 *ad lib*, all other assessments will be done after T_0 *ad lib*, at 10 minutes \pm 2 minutes, at 20 minutes \pm 2 minutes, 30 minutes \pm 5 minutes, 40 minutes \pm 5 minutes, 1 hour, 2 hours, 4 hours \pm 10 minutes each.
- m. The adapted mCEQ and SQ questionnaires will be answered within 60 minutes after the end of the *ad libitum* use period.
- n. VAS, three Likert scales and one open question. The cough questionnaire will be completed at Admission prior to product test and 24 hours (\pm 1 hour) after T_0 fix for each variant (but prior to next variant use).
- o. Spontaneous reporting of new AEs/SAEs by the subject and follow-up of ongoing AEs/SAEs by the site.
- p. All P3P products will be weighed before and after use.
- q. All examinations listed at Discharge, with the exception of blood sampling for nicotine measurement and cough assessment, should also be conducted in subjects prematurely terminating the study (early termination procedures).

Confidentiality Statement

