3.2 Secondary Objectives and Endpoints

1. To evaluate the plasma concentration-time profile of nicotine and derived PK parameters (with and without adjustment for baseline nicotine concentrations) of the four P3P variants from the *ad libitum* use period.

Endpoints:

- Plasma nicotine concentration-time profile
- Peak plasma nicotine concentration [C_{peak}]
- Time to peak plasma nicotine concentration [t_{peak}]
- Trough plasma nicotine concentration [C_{trough}]
- Average of plasma nicotine concentration from T_0 ad lib to 1 hour [$C_{average}$]
- Area under the concentration-time curve from start of product use (T_0 ad lib) to 4 hours [$AUC_{ad\ lib\ (0-4h)}$]

2. To evaluate the pharmacodynamic effects (subjective effects and related behavioral assessments) of four P3P variants.

Endpoints:

- Visual Analogue Scale (VAS)-craving assessment from the fixed puffing regimen and *ad libitum* use period
- Product evaluation by an adapted version of the modified Cigarette Evaluation Questionnaire (adapted mCEQ) following the *ad libitum* use period
- Sensory Questionnaire (SQ) following the *ad libitum* use period

Confidentiality Statement

Data and information contained in this document are considered to constitute trade secrets and confidential commercial information, and the legal protections provided to such trade secrets and confidential information are hereby claimed under the provisions of applicable law. No part of this document may be publicly disclosed without the written consent of Philip Morris Products S.A.

3. To evaluate human puffing topography of four P3P variants during the fixed puffing regimen and the *ad libitum* use period.

Endpoints:

- Per-puff parameters and per-product use experience parameters

4. To estimate the amount of powder aerosolized from P3P from the fixed puffing regimen and the *ad libitum* use periods.

Endpoints:

- Weight difference of P3P before and after use

5. To monitor the safety and tolerability during the study.

Endpoints:

- Incidence of adverse events (AEs), serious adverse events (SAEs)
- Frequency of AEs, SAEs
- Incidence of P3P product events including malfunction/misuse
- Frequency of P3P product events including malfunction/misuse
- Physical examination changes from baseline
- Cough changes from baseline (VAS and three Likert scales)
- Electrocardiogram (ECG) changes from baseline (heart rate, PR, QRS, QT, QTcB, QTcF intervals)

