6.2.1 Admission (Day -1)

After enrollment, subjects will be required to perform product test using up to three P3P 3 products. Subjects will be instructed to use P3P in a similar way to their own cigarette i.e. with a 2-step process with 1) puffing and 2) inhalation. They will be asked to puff with sufficient intensity to trigger the spinning of the capsule. The subject should hear the sound of the capsule spin and/or feel the vibration of the product induced by the spinning.

After the product test, subjects unable to use the product as specified (i.e. trigger the spinning of the capsule) as well as subjects not willing and/or unable to use P3P will be discontinued from the study and will enter a 7-day Safety Follow-Up Period.

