7.8.5 Cough Assessment

Subjects will be asked if they have experienced a regular need to cough, e.g., whether they have coughed several times in the previous 24 hours prior to assessment. If the answer is 'yes', they will be asked to complete a cough assessment questionnaire (which includes a VAS, three Likert scales, and an open question).

The VAS will assess how bothersome cough is to the subject ranging from 'not bothering me at all' to 'extremely bothersome'.

Furthermore, subjects will be asked to assess the intensity and frequency of cough and the amount of sputum production on Likert scales:

- The intensity of cough will be assessed on a 5-point Likert scale ranging from 1 to 5:
1 = very mild; 2 = mild; 3 = moderate; 4 = severe; 5 = very severe.
- The frequency of cough will be assessed on a 5-point Likert scale ranging from 1 to 5:
1 = rarely; 2 = sometimes; 3 = fairly often; 4 = often; 5 = almost always.
- The amount of sputum production will be assessed on a 4-point Likert scale ranging from 0 to 3:
0 = no sputum; 1 = a moderate amount of sputum; 2 = a larger amount of sputum; 3 = a very large amount of sputum.

Cough assessment will be conducted at Admission prior to product test and 24 hours (± 1 hour) after product use (T_0 fix) for each variant (Day 2 through Day 5). Cough assessment should be done in the morning prior to any product use.

Confidentiality Statement

Data and information contained in this document are considered to constitute trade secrets and confidential commercial information, and the legal protections provided to such trade secrets and confidential information are hereby claimed under the provisions of applicable law. No part of this document may be publicly disclosed without the written consent of Philip Morris Products S.A.

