9.4 Day of Discharge

The assessments in Table 11 will be conducted prior to the time of Discharge on Day 5:

Table 11 Time Schedule – Day of Discharge (Day 5)

Blood Sample	Procedures	Additional Information
	Support during periods of smoking abstinence	Ongoing
✓	Clinical laboratory parameters (hematology, clinical chemistry)	After at least 6 hours of fasting.
	Urine analysis safety panel	
	Cough assessment	24 ± 1 hours after T_0 _{fix} for the product used on the previous day
	Breakfast	
✓	Blood sampling for determination of subject's nicotine $t_{1/2z}$	Blood will be drawn at the following time points post T_0 _{ad lib} for the product used on Day 4: T1 after 14 hours ± 30 minutes, T2 after 16 hours ± 30 minutes,

Confidentiality Statement

Data and information contained in this document are considered to constitute trade secrets and confidential commercial information, and the legal protections provided to such trade secrets and confidential information are hereby claimed under the provisions of applicable law. No part of this document may be publicly disclosed without the written consent of Philip Morris Products S.A.

Blood Sample	Procedures	Additional Information
		T3 after 18 hours \pm 30 minutes, T4 after 20 hours \pm 30 minutes, T5 after 24 hours \pm 30 minutes.
Lunch		
Urine pregnancy test (all female subjects)		
Vital signs (blood pressure, pulse rate, respiratory rate)		At least 5 min in supine position prior to measurement.
ECG		After resting for at least 10 min in supine position prior to recording.
Spirometry		After resting in sitting position for at least 15 minutes.
Physical examination		
Information on risks of smoking, smoking cessation advice and product debrief		
AE/SAE, concomitant medication recording		
Discharge		

Abbreviations: AE = Adverse event; ECG = Electrocardiogram; SAE = Serious adverse event

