9.6 Early Termination Procedures

When a subject is discontinued from the study, all early termination procedures listed below are performed unless the subject refuses to perform the assessments.

Confidentiality Statement

Data and information contained in this document are considered to constitute trade secrets and confidential commercial information, and the legal protections provided to such trade secrets and confidential information are hereby claimed under the provisions of applicable law. No part of this document may be publicly disclosed without the written consent of Philip Morris Products S.A.

Table 12 Time Schedule – Early Termination

Blood Sample	Procedures	Additional Information
✓	Clinical laboratory parameters (hematology, clinical chemistry) Urine analysis safety panel Urine pregnancy test (all female subjects) Vital signs (blood pressure, pulse rate, respiratory rate) ECG Spirometry Physical examination Information on risks of smoking, smoking cessation advice and product debrief	At least 5 min in supine position prior to measurement. After resting for at least 10 min in supine position prior to recording. After resting in sitting position for at least 15 minutes.
	AE/SAE, concomitant medication recording	
	Discharge	

Abbreviations: AE = Adverse event; ECG = Electrocardiogram; SAE = Serious adverse event

Confidentiality Statement

Data and information contained in this document are considered to constitute trade secrets and confidential commercial information, and the legal protections provided to such trade secrets and confidential information are hereby claimed under the provisions of applicable law. No part of this document may be publicly disclosed without the written consent of Philip Morris Products S.A.

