### **12.6.5.5.6 Assessment of Cough**

Cough questionnaire is assessed on Day -1 prior to product test and prior to product use on Day 2, 3, 4 and 5. Questionnaire details are reported in Section 7.3.5 "Cough Assessment".

The answer to the Cough questionnaire will be listed (Listing 15.3.6.11).

The number and % of subjects reporting a cough will be summarized at baseline and after product use. The responses to the individual items, including the VAS evaluating the level of cough bother and 3 Likert scales measuring the intensity, the frequency of cough and the amount of sputum production will be listed and summarized at baseline and change from baseline by P3P variant, for all subjects who filled in the questionnaire. The answers to the open question related to any other important observation will be listed only (Table 15.2.6.19).

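### Cough is left out of early termination, so a subject who leaves the study between using a variant and the next-morning assessment has no VAS or Likert cough score for that variant.

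*Protocol*

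**What the plan says.** Protocol section 3.2 lists "Cough changes from baseline (VAS and three Likert scales" among the safety and tolerability endpoints.

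On timing, Protocol section 7.8.5 says: "Cough assessment will be conducted at Admission prior to product test and 24 hours" (with a 1-hour tolerance) after T0 fix of each variant, on Days 2 to 5. It adds: "Cough assessment should be done in the morning prior to any product use". Table 11 (Day 5) ties the Discharge score to T0 fix "for the product used on the previous day".

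On early termination, footnote q of Appendix A repeats the Discharge examinations "with the exception of blood sampling for nicotine measurement and cough assessment, should also be conducted". The notes to the schedule in SAP section 16.1 carry the same exception. Table 12 in Protocol section 9.6 agrees with it: apart from blood tests and AE and medication recording, it names "Urine analysis safety panel Urine pregnancy test (all female subjects) Vital signs (blood pressure, pulse rate, respiratory rate) ECG Spirometry Physical examination", and no cough item. Under Protocol section 5.2 these procedures apply to every discontinued subject who was exposed to P3P, unless the subject refuses.

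On analysis, SAP section 12.6.5.5.6 gives the number and percentage reporting a cough. It summarises the VAS and Likert items by variant "for all subjects who filled in the questionnaire".

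**The concern.** Of the two measures exempted at early termination, nicotine sampling is a PK measurement. Cough is the only safety examination that is dropped, and no reason is given. For an inhaled powder, cough is also one of the more likely reasons for a subject to leave. The scores most likely to be lost are then the high ones, and the loss falls on the variant that provoked them. The comparison of tolerability between variants would be flattered in favour of the worst tolerated. Subjects lost after randomization are not replaced, so the gap is not refilled.

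**Working it through.** No sample-size or power figure bears on this point. The only stated number used is 18 randomized subjects, which is 6 sequences × 3.

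**Step 1. Discharge against early termination.**

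| Item | Table 11 (Discharge) | Table 12 (early termination) |
|---|---|---|
| Hematology, chemistry, urine panel | yes | yes |
| Pregnancy test | yes | yes |
| Vital signs, ECG, spirometry | yes | yes |
| Physical examination | yes | yes |
| AE and medication recording | yes | yes |
| Cough assessment | yes | no |
| Nicotine PK samples | yes | no |

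**Step 2. When a score is lost.** Product use starts at about the same time each day (Protocol section 4.1), so successive T0 fix are about 24 h apart. The score is due from 24 − 1 = 23 h after T0 fix and, on Days 2 to 4, before the next use. A subject who leaves within about 23 h of T0 fix has no score for that variant. One who is assessed in the morning and then leaves before the next use keeps it.

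**Step 3. Whether anything else supplies the score.** SAP Table 16 gives an early-termination row for vital signs but none for cough. SAP section 12.6.5.5.6 names only Day -1 and Days 2 to 5. Protocol section 12.1.4 says missing data are in general not imputed. SAP section 12.1.5 sets the VAS to zero when no cough was reported at a visit, without separating a subject who was asked and answered no from one who was not asked.

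**Step 4. How the loss would be displayed.** SAP section 12.1.3 makes missing values a category of their own for categorical data. Protocol section 12.1.3 and SAP section 12.1.3 also require the number and percentage with missing data. A subject without a score should therefore appear as missing.

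**Step 5. Size, by illustration only.** Let k subjects with cough leave before assessment and x other subjects have cough, out of 18. The counts are assumptions.

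- Share with complete data: (x + k)/18.
- Share shown with a missing category: x/18. The shortfall is k/18, which is 5.6, 11.1 and 16.7 percentage points for k = 1, 2 and 3.
- Example with x = 2, k = 2: 4/18 = 22.2% with complete data. The table shows 2/18 = 11.1% cough, 14/18 = 77.8% no cough and 2/18 = 11.1% missing.
- Mean VAS (0 to 100), with k = 1 and subjects without cough scored zero: two assessed subjects at 30 and fifteen at 0 give 60/17 = 3.5. Adding a leaver at 50, 80 or 100 gives 110/18 = 6.1, 140/18 = 7.8 or 160/18 = 8.9.

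The denominator of 18 fits P3P 1, 2 and 4. P3P 3 may have more users, because replaced and supernumerary subjects also use it on Day 1.

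**The case against.** The strongest reply is that cough ending participation is not hidden. AEs are the primary safety assessment. Protocol section 8.2.1 requires every AE to be documented, Table 12 keeps AE recording, and the SAP tabulates AEs by exposure period and lists those leading to discontinuation (sections 12.6.5.1, 12.6.5.2 and 12.6.5.2.2). This stands: what is lost is the scored endpoint, not all information on cough. A reader might infer from Protocol section 7.8 that such cough could go unrecorded, since it makes AE entry of questionnaire symptoms discretionary. That discretion covers symptoms documented on a questionnaire, and these subjects have no post-use questionnaire.

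A reader might also infer that leavers drop silently out of numerator and denominator, giving 2/16 = 12.5% in the example. The SAP does not say so. The restriction to those who completed the questionnaire qualifies the VAS and Likert summaries, not the count of subjects with cough, and the missing-value rules in Step 4 apply.

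Nor does every subject who stops because of cough lose a score. Protocol sections 6.2 and 6.2.4 allow a subject to reduce or stop product use without leaving the study, and anyone still confined is assessed the next morning.

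The product test on Day -1 is a weaker case than it looks. After it, subjects unable to use the product as specified, "as well as subjects not willing and/or unable to use P3P will be discontinued from the study". But no one, including those who continue, has a score tied to the product test alone, so the schedule creates no difference between leavers and continuers there.

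The 24-hour anchor may itself explain the exclusion, although the documents do not say so. A previous-24-hours question put 2 h after T0 fix on Day 3 would cover 24 − 2 = 22 h before that use, including the previous day's variant. This is a fair objection to reusing the question unchanged, but not to asking about cough at all.

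Finally, the study is a descriptive pilot with no hypotheses and a low expected drop-out rate. That limits the stakes.

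**Conclusion.** The point holds within limits. The documents consistently omit cough from early termination. A subject who leaves on Days 1 to 4 after using a variant and before the next-morning assessment has no VAS or Likert score for that variant. Because cough can cause the exit, the missingness can depend on the outcome. In that case the reported share with cough and the scores are understated.

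The amount cannot be estimated, because the documents give no cough rate and no drop-out rate. The shortfalls above rest on assumed counts and on the leavers having had cough. The documents do not support reading this as a concealed loss or as a loss of all cough data. Nor do they support a confirmed bias of known size. It is a gap in a secondary tolerability endpoint that is worth closing because closing it costs little.

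**What to change.** **Protocol.** Delete the words exempting cough from footnote q of Appendix A and from the SAP section 16.1 copy. Add the cough questionnaire to Table 12 for subjects who terminate on Days 1 to 4 after using a variant and before its next-morning assessment. Word the question as covering the time since first use of that day's variant (T0 fix), not the previous 24 hours, and record the time elapsed since T0 fix.

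**SAP.** Show these scores by variant as a separate early-termination time point, and give a summary that includes them beside the scheduled one. State in section 12.1.5 that a cough assessment not done is missing and is not set to VAS zero. Report the number not assessed for each variant. If a score is ever collected after the Day -1 product test, report it only under the Product Test Period.

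**Cost.** One yes/no question and a short paper questionnaire at a visit that already takes place, with no extra staff or samples. The downside is a recall period shorter than 24 h that differs between subjects, which is why the scores should be shown separately. If data collection has closed, the missing-not-zero rule and the counts not assessed can still be added to the SAP.
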